Analysis Metric: Time to event, measured from the initial patient visit to the time genetic testing is conducted.

Method of Aggregation: Median time in days

Specific Measurement Variable: Rates of genetic testing. **Analysis Metric:** Proportion of patients who received testing **Method of Aggregation:** Proportion of patients, presented as a percentage

Time Point: Assessed after one year to include enough time for patients to undergo testing through the usual course of care.

Specific Measurement Variable: Diagnosis via any genetic testing.

Analysis Metric: Proportion of patients diagnosed with a genetic disease following molecular testing or clinical evaluation. **Method of Aggregation:** Proportion of patients, presented as a percentage.

Time Point: Assessed after one year to include enough time for patients to undergo additional testing through usual care.

Specific Measurement Variable: Adherence to the SIGHT-prompted provider message.

Analysis Metric: Frequency of provider actions via referral to genetics and ordering a patient CMA following receipt of a SIGHT-prompted message.

Method of Aggregation: Proportion of instances where the provider follows the SIGHT recommendation.

Time Point: Information will be collected at the end of the study.

Participant timeline

- Time schedule of enrolment, interventions (including any run-ins and washouts), assessments, and visits for participants. A schematic diagram is highly recommended (see Figure)
 - 1. Enrollment Process: Eligibility Screening: Conducted at the initial patient visit. Consent Process: Following eligibility screening, informed consent will not be obtained as patients are following usual care.
 - **2. Interventions:** SIGHT-Prompted Provider Message: Initiated following screening for patients who meet the predefined risk threshold.
 - 3. Assessments: Baseline Assessment: Conducted during the initial visit, including collection of patient health data. Follow-up Assessments: Scheduled after initial visit to monitor the outcomes, such as number of patients receiving a diagnosis, time to genetic testing, and diagnostic yield.
 - 4. Visits: Initial Visit: SIGHT prompted provider message followed by review of referrals and documentation attributable to the initial patient visit. Subsequent Visits: Regular follow-ups as per usual pediatric care, during which recommendations and any genetic testing decisions are documented and assessed.

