The statistical analysis will utilize a chi-square test for binary outcomes such as the presence or absence of a genetic diagnosis as identified by the test or provider adherence to SIGHT message recommendations. For continuous secondary outcomes, such as the time to genetic testing, a T-test or Mann-Whitney U test will be used depending on data distribution. Subgroup analyses will involve regression methods to assess the differential effects of the intervention across subgroups defined by baseline demographic characteristics (e.g. age, sex, race). Multivariate analyses will be conducted using logistic regression for binary outcomes and linear or Cox proportional hazards regression for continuous or time-to-event outcomes, respectively. Model assumptions will be checked through the assessment of residuals and model fit will be evaluated accordingly.

When indicated, a two-sided p-value of less than 0.05 will be considered statistically significant. The Bonferroni correction will be applied to account for multiple comparisons when analyzing multiple outcomes. R will be used to perform all analyses. The analysis plan will follow the intention-to-treat principle, with all randomized participants included in the analysis according to the group to which they were allocated.

Variable/outcome	Hypothesis	Outcome measure	Methods of analysis
Primary			R will be used to perform all analysis.
Number of diagnoses via CMA	More patients are diagnosed being flagged by SIGHT via a Chromosomal Microarray	Number of patients flagged by SIGHT who receive a diagnosis via CMA over one year vs controls [binary]	Chi-square test
Secondary			
a. Time to genetic test	Patients in the intervention arm will receive genetic testing faster than those in the controlarm.	Duration in days for which patients flagged by SIGHT receive a genetic test vs control [continuous]	Cox proportional Hazards to compare the time to event (in this case genetic testing) between two groups while controlling for covariates.
b. Rates of genetic testing	Increased rates of genetic testing in the intervention arm	Rates of genetic testing ordered by providers between cases and controls over a one-year period after POD-C visit [continuous'	Binary logistic regression to calculate the odds ratio for the likelihood of receiving a genetic test in the intervention arm compared to the controls

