c. Diagnosis via any test (molecular confirmation)	More patients will receive a diagnosis from molecular confirmation outside of firs tier testing via a CMA.	Number of patients flagged by SIGHT who receive a diagnosis via any test over one year vs controls [binary]	Chi-square test
d. Adherence to Intervention	Providers who Receive SIGHT prompts demonstrate higher adherence recommendations compared to controls	Proportion of eligible patients where providers ordered a CMA and place genetics referrals after receiving a prompt [binary]	Chi-square test; logistic regression adjusting for covariates

20b Methods for any additional analyses (eg, subgroup and adjusted analyses)

Subgroup analysis within demographic groups (sex, race, age) will be performed as described in the primary analysis but within each group or stratified by age.

Definition of analysis population relating to protocol nonadherence (eg, as randomised analysis), and any statistical methods to handle missing data (eg, multiple imputation)

Non-adherence and missing data for the SIGHT protocol are non-applicable in this context as patients will follow usual care. Patients who are lost to follow up or have no follow up care during the duration of the study will remain included in the analysis.

Methods: Monitoring

Data monitoring 21a

Composition of data monitoring committee (DMC); summary of its role and reporting structure; statement of whether it is independent from the sponsor and competing interests; and reference to where further details about its charter can be found, if not in the protocol. Alternatively, an explanation of why a DMC is not needed.

This study does not require a DMC as the protocol presents minimal risks to participants and adverse events or other problems are not anticipated. In the unlikely event that such events occur, unanticipated problems involving risks to subjects or others will be reported immediately to the PI and and within 7 days of the PI's notification of the event to the IRB.

21b Description of any interim analyses and stopping guidelines, including who will have access to these interim results and make the final decision to terminate the trial

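### Time to genetic testing has conflicting analyses in section 20a, and the T-test/Mann-Whitney named in the prose does not suit an outcome that about 91% of controls are expected not to reach

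*Protocol*

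**What the plan says.** Four statements in the protocol bear on this outcome.

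- **Section 20a, prose.** "For continuous secondary outcomes, such as the time to genetic testing, a T-test or Mann-Whitney U test will be used", the choice depending on the data distribution. A later sentence in the same paragraph covers multivariate analyses: linear regression for continuous outcomes and Cox regression for time-to-event outcomes.
- **Section 20a, table, secondary outcome a.** The only method listed is "Cox proportional Hazards to compare the time to event (in this case genetic testing) between two groups while controlling for covariates". The outcome measure in that row is tagged as continuous.
- **Section 12.** The analysis metric is "Time to event, measured from the initial patient visit to the time genetic testing is conducted" and the aggregation is "Median time in days". No time point is given for this outcome, whereas the testing-rate outcome is assessed at one year.
- **Analysis population.** Section 20a calls for intention to treat, "with all randomized participants included in the analysis according to the group to which they were allocated". The item on analysis population and missing data adds: "Patients who are lost to follow up or have no follow up care during the duration of the study will remain included in the analysis".

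On multiplicity, section 20a states: "The Bonferroni correction will be applied to account for multiple comparisons when analyzing multiple outcomes". It gives no divisor.

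**The concern.** The two methods are not interchangeable here. A Cox model uses every randomized patient and treats those never tested as censored. A T-test or Mann-Whitney test needs a number of days for each patient, and an untested patient has none unless a rule supplies one. The protocol supplies no such rule.

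If the prose is followed on observed days, the analysis keeps only tested patients. Being tested is what the provider message is meant to change (secondary outcome b), so the two groups compared are selected after randomization. The question also changes, from whether patients in the SIGHT arm reach testing sooner to whether those who were tested had it sooner. A message that greatly increases testing could then show no difference in time to testing.

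Faster testing is a stated objective of the trial. With two methods that can disagree and no statement of which one decides, the choice could be made after the data are seen.

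**Working it through.** **Inputs from the protocol (section 14).** 500 patients per arm; 9% of high-risk patients tested under usual care; 9% of those diagnosed; target diagnosis rate 3.6%. The protocol's own product reproduces: 0.09 × 0.09 = 0.0081, or 0.81%. The protocol states no power for time to testing, so there is no such figure to reproduce.

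**Patients without a test time.**
- Controls: 500 × (1 − 0.09) = 455, leaving 45 with a value.
- SIGHT arm: the testing rate is not stated. If the 9% yield also held there (assumption), the 3.6% target implies 0.036 / 0.09 = 40% tested.
- Share of all 1,000 without a time = 1 − (0.09 × 500 + p × 500) / 1000. This is 91% at p = 0.09, 85.5% at 0.20, 75.5% at 0.40 and 70.5% at 0.50.

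**Median.** Over all randomized patients the median time is reached only if at least half of an arm is tested. It is not reached in controls at 9%, nor in the SIGHT arm at 40%.

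**Simulation (timings assumed; the documents give none).** 500 per arm, 4,000 runs per setting, two-sided 0.05. Controls: 9% tested, uniform over days 0–365. SIGHT arm: the same 9% plus prompted tests, bringing the total to 20%, 40% or 50%.

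| Timing of prompted tests | Mann-Whitney, tested patients only | 20% / 40% / 50% tested |
|---|---|---|
| Days 0–365 (as controls) | significant in either direction | 4.8% / 5.1% / 5.0% |
| Days 0–180 | SIGHT faster | 77.3% / 97.8% / 98.9% |
| Days 90–365 | SIGHT slower | 25.4% / 51.3% / 57.7% |

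Across these nine settings, a log-rank test on all randomized patients favours SIGHT in at least 99.8% of runs. So does a Mann-Whitney test that ranks untested patients last. At 0.0125 (an assumed Bonferroni division over the four secondary rows), the same-timing figures for the tested-only test fall to 1.1% / 1.1% / 1.5%. The two all-randomized tests stay at or above 99.2%.

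**Second timing model.** Exponential times with censoring at 365 days, 2,000 runs, SIGHT arm 15% / 18% / 25% / 40% tested. The tested-only Mann-Whitney rejects in 4.8% / 4.3% / 6.6% / 11.5%, the log-rank test in 83.8% / 98.8% / 100% / 100%. The T-test on tested patients behaves almost identically to the Mann-Whitney.

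**How far the slower result depends on timing.** In a separate rerun, starting prompted tests at day 90 gave SIGHT significantly slower in 27% / 51% / 58% of runs. Starting at day 30 gave 6% / 12% / 11%, and days 30–270 gave under 0.5%.

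**The case against.** The best defence is that the paragraph runs from simple tests to regression models and names Cox for time-to-event outcomes, which is what section 12 calls this one. The table row is the most specific entry and lists Cox alone. On that reading the T-test or Mann-Whitney is an unadjusted companion to an adjusted Cox model. Much of this stands: the text does lean toward Cox, and it would be wrong to say that the prose offers only the simple tests. But the reading is not stated. Row d of the table spells out such a pair, "Chi-square test; logistic regression adjusting for covariates", and row a does not. Because both prose and table call the outcome continuous, the regression sentence could equally send it to linear regression. Even as a companion, the simple test has the problem shown above.

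A second defence is that intention to treat already forbids dropping untested patients, so the harmful version is excluded. That rule does conflict with a tested-only comparison, but it does not say what value an untested patient receives. A detailed scoring rule could be left to an analysis plan. Two competing methods in the protocol cannot, since any analysis plan would have to override one of them.

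Two stronger readings are tempting. A reader might infer that the simple tests cannot be rescued. They can: scoring every untested patient at one year makes either test usable. For the T-test it favoured SIGHT in 94–100% of runs at 0.05 in a rerun of the nine settings. The protocol just does not state that rule. A reader might also infer that the prose test would reverse a real benefit. That needs prompted tests to come markedly later than usual-care tests, and nothing in the documents says they will.

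**Conclusion.** The point holds as an inconsistency that should be resolved before analysis. Section 20a gives conflicting analyses for time to genetic testing without naming the deciding one. The simple tests, applied to observed days, would leave out about 91% of controls and can miss a large effect almost entirely: about 5% rejection against over 99% when test timing is alike in both arms and 20% or more of the SIGHT arm is tested. If prompted tests come early, the tested-only comparison usually does find SIGHT faster, so the loss depends on timing.

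The 91% is a planning figure, because the protocol gives no time window for its 9%. The SIGHT-arm testing rates, the timings and the 0.0125 level are assumptions. The consequences are confined to this secondary outcome. The primary chi-square test and the sample size are untouched.

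**What to change.** In section 20a, remove time to genetic testing from the T-test/Mann-Whitney sentence and relabel row a as time-to-event. State that the Cox model already in that row is the single deciding analysis. It should include all randomized patients by allocated arm, timed from the initial POD-C visit in both arms, with untested patients censored at one year.

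Flag the one-year limit as an addition. Section 12 sets no time point for this outcome, and one year matches the testing-rate outcome.

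Do not censor at the last health-record entry in the main analysis. Later records can depend on care that the message itself triggers, and a patient with no later visit would contribute almost no time at risk. Use that rule only as a sensitivity analysis.

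In section 12, report the cumulative proportion tested by arm through one year. If a median is kept, label it as descriptive among tested patients.

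The cost is wording in sections 12 and 20a and a little extra analysis. The sample size, the primary analysis and trial conduct do not change.

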Healthcare providers of the patients in the SIGHT-guided intervention arm will receive alert messages, recommending consideration of genetic testing and referral to the genetics clinic. In contrast, providers of the patients in the standard care arm will not receive such alerts and will proceed with usual care practices. Patients with a score greater than equal to 0.30 and who have a scheduled visit at POD-C will be randomized in a 1:1 ratio to either the usual care or SIGHT-guided arm. Randomization will be stratified within the VUMC pediatric POD-C clinic. Patients will be excluded if they have already undergone Chromosomal Microarray testing at VUMC.

Objectives 7 Specific objectives or hypotheses

This study will evaluate the effectiveness of SIGHT as a clinical support system to prompt provider/patient discussion and shared decision making regarding the need for genetic testing in form of a chromosomal microarray. We seek to study if identifying patients with high SIGHT scores will decrease the duration of time to testing and increase diagnostic yield. SIGHT only relies on data already collected in routine clinical encounters and is calculated prior to a clinical visit at VUMC.

SIGHT does not replace clinical judgment in determining the necessity for genetic testing, but we seek to measure whether SIGHT increases the rates at which the important problem of elucidating the genetic etiology of disease is addressed. Our SIGHT-guided intervention group will be patients with high SIGHT scores where their provider receives a clinical communication recommending ordering of a genetic test and referral to the genetics clinic. Our comparison group will be patients with equivalently high SIGHT scores that receive usual care (i.e., do not receive a provider message). Patients will be from the POD-C pediatric primary care clinic at the Vanderbilt University Medical Center (VUMC) One Hundred Oaks location (OHO).

Trial design

8

Description of trial design including type of trial (eg, parallel group, crossover, factorial, single group), allocation ratio, and framework (eg, superiority, equivalence, noninferiority, exploratory)

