The allocation sequence will be generated by the study's data management team using a computer-based randomization function. Any pediatric patient scheduled for a visit in the POD-C pediatric primary care clinic at VUMC One Hundred Oaks (OHO) who meets or exceeds the predefined risk threshold will be flagged as eligible. These flagged patients will then be randomly assigned to either the intervention arm (SIGHT-prompted provider message) or the usual care arm (no provider message).

Participant Enrollment

Patients aged 1 to 20 years who have not previously undergone chromosomal microarray testing at VUMC will be automatically included in the randomization pool once they have a scheduled visit at the OHO clinic. As this study follows standard clinical care, patients themselves do not undergo a separate consent process for randomization. Instead, their providers will be informed of any SIGHT alerts only if the patient is randomized to receive them.

Assignment of Participants to Interventions

For those randomized to the intervention arm, a SIGHT-prompted provider message is generated within EPIC by a genetic counselor on the research team. This message indicates the patient's increased risk level and recommends considering a chromosomal microarray and referral to genetics. The provider maintains full discretion to act upon or dismiss this recommendation. By contrast, providers in the usual care arm receive no automated messages about SIGHT risk, and patients continue under routine care practices.

Concealment of Allocation

The randomization process is integrated into the workflow so that neither providers nor the study team can predict a patient's assignment prior to the system's automated allocation. This design ensures there is no foreknowledge of group assignment—preventing selection bias and preserving the trial's integrity.

Blinding (masking)

17a

Who will be blinded after assignment to interventions (eg, trial participants, care providers, outcome assessors, data analysts), and how

There will be no blinding of participants or physicians as patients and providers will follow usual care. Providers may dismiss the SIGHT – prompted provider message and not act on its recommendations at any time. No other intervention is planned. Patients would be unaware of the providers' decisions in that case unless the provider chooses independently to discuss the SIGHT score with them.

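### Secondary outcome d (adherence) is tested against controls, but its event requires a prompt that controls never receive

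*Protocol*

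**What the plan says.** Row d of the Protocol's item 20a table has three parts that need to agree.

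- Hypothesis: "Providers who Receive SIGHT prompts demonstrate higher adherence recommendations compared to controls".
- Outcome measure: "Proportion of eligible patients where providers ordered a CMA and place genetics referrals after receiving a prompt [binary".
- Methods: a chi-square test, plus logistic regression with covariates.

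The item 20a text also lists "provider adherence to SIGHT message recommendations" among the binary outcomes for chi-square testing, and requires intention-to-treat analysis of everyone randomised.

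Item 12 defines the same outcome as "Frequency of provider actions via referral to genetics and ordering a patient CMA following receipt of a SIGHT-prompted message", aggregated as "Proportion of instances where the provider follows the SIGHT recommendation". It mentions no comparison with controls.

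On who is messaged, item 6b states that "providers of the patients in the standard care arm will not receive such alerts", and item 16c that "providers in the usual care arm receive no automated messages about SIGHT risk".

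**The concern.** The event is conditional on something that happens in one arm only. A control patient whose provider orders a microarray and refers to genetics has had exactly the same care as an adherent SIGHT-arm patient. The definition nevertheless counts that patient as a non-event, or leaves the patient out of the denominator. The comparison then shows that messages were sent in one arm and not in the other, which is already known. It does not show whether the message changed what providers did.

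The risk is a published, highly significant adherence effect produced by the definition, or an unplanned redefinition once the data are in hand. The trial is open-label, so the event, its start date and its window should be settled beforehand.

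**Working it through.** The Protocol gives no numerical figure for outcome d, so there is none to reproduce.

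**Inputs**
- 500 patients per arm (item 14).
- Two-sided 0.05 (item 20a).
- Bonferroni correction across multiple outcomes, family not named (item 20a). I assume the four secondary outcomes, so 0.05/4 = 0.0125.
- Usual-care genetic testing rate of 9% in high-risk patients (item 14), used only as a proxy. No rate for order plus referral is given, so I take 1% to 9%.

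**Step 1: what the control arm must be.** The event requires a prompt, and controls have none. With eligible patients as denominator (item 20a) the control arm is 0/500. With instances of a message as denominator (item 12) it is 0/0, and neither planned test can be computed.

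**Step 2: how few SIGHT-arm events reach significance against 0/500.** For x/500 against 0/500:

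- uncorrected chi-square = 1000x / (1000 − x)
- continuity-corrected chi-square = 1000(x − 1)² / [x(1000 − x)]

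The critical values are 3.84 (0.05) and 6.24 (0.0125).

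| Test | Level | Just short | First to reject |
|---|---|---|---|
| Uncorrected | 0.05 | x = 3: 3.01 | x = 4: 4.02 (p = 0.045) |
| Corrected | 0.05 | x = 5: 3.22 | x = 6: 4.19 (p = 0.041) |
| Uncorrected | 0.0125 | x = 6: 6.04 | x = 7: 7.05 (p = 0.0079) |
| Corrected | 0.0125 | x = 8: 6.17 | x = 9: 7.18 (p = 0.0074) |

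Fisher's exact test also needs 6 events at 0.05 (p = 0.031), and 8 at 0.0125.

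**Step 3: chance of rejection when the message changes nothing.** Suppose providers order and refer for the same share r of patients in both arms, but control actions are not counted. The chance of rejection is P(Binomial(500, r) ≥ minimum x).

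| r (assumed) | 0.05, uncorrected / corrected | 0.0125, uncorrected / corrected |
|---|---|---|
| 1% | 74% / 38% | 24% / 7% |
| 2% | 99% / 93% | 87% / 67% |
| 3% | 99.98% / 99.7% | 99.3% / 96% |
| 9% | >99.99% / >99.99% | >99.99% / >99.99% |

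At r = 9% the expected table is 45/500 against 0/500, with p about 7 × 10⁻¹².

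**Step 4: the same test with the event counted alike in both arms.** At 9% in each arm, exact enumeration of the uncorrected chi-square at 0.05 gives a rejection rate of 5.0%. The excess in step 3 therefore comes entirely from the definition.

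**Step 5: the logistic regression.** With no control events and a mixture in the SIGHT arm there is quasi-complete separation. Fitted to 45/500 against 0/500, the model did not converge. When the fit stopped, the arm log-odds ratio was 21.3 with standard error 6,078. No finite maximum-likelihood estimate exists, and adding covariates does not supply one.

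**The case against.** The strongest reply is that this is loose drafting. Item 20a says that outcomes compare the two arms. Item 18a collects microarray orders, referrals and dates, and has them verified by chart review in both arms. Item 17a uses a test-referral rate across all patients. Surely controls would be scored on the same actions. That may be the intent, but no section says so for outcome d, and item 12 repeats the condition of a received message. The item 17a rate serves only the sample size re-estimation and is not spelled out. An analyst who follows the text gets zeros. One who departs from it must choose the event and window unguided.

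Several further points stand in part:

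- The percentages in step 3 are not type I error for the event as literally defined, since under that definition the arms do differ. They show how often the test would reject when provider behaviour is the same.
- They rest on assumed rates, and at 1% with the 0.0125 level they fall to 24% / 7%.
- The four-event threshold uses the uncorrected test where expected counts are only 2 per arm. Six is the sturdier figure.
- Item 12, read alone, is a coherent measure for the SIGHT arm. The conflict comes from the comparison attached in item 20a.
- Adherence is not among the key secondary outcomes in the registration table. Outcome b already compares "Rates of genetic testing ordered by providers between cases and controls over a one-year period after POD-C visit" without mentioning a prompt. It does not include referrals, however, so it does not repair d.

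**Conclusion.** The concern holds. Row d sets a between-arm test on an event that one arm cannot have, and nothing elsewhere in the Protocol supplies a definition that works in both arms. As worded, 4 to 6 SIGHT-arm events (0.8% to 1.2% of 500) suffice for p < 0.05, or 7 to 9 at an assumed Bonferroni level of 0.0125. With identical provider behaviour, rejection at 0.05 is close to certain once the true order-plus-referral rate is about 2% or more.

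This rests on the literal wording, 500 patients per arm being reached, and the assumed rates. The contradiction itself depends on none of the numbers. The primary analysis, the sample size and secondary outcomes a to c are unaffected. It should be corrected, but it does not threaten the trial's main conclusion.

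**What to change.** Report adherence in the SIGHT arm only. Give the proportion of messaged patients with a microarray order, with a genetics referral, and with both, each with a 95% confidence interval and no between-arm test. Use messaged patients as the single denominator in item 12 and in the item 20a text and table, and remove the comparison with controls from row d.

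If a comparison between arms is wanted, define it without reference to a prompt and identically in both arms. An example is a microarray ordered and a genetics referral placed within one year after the index POD-C visit, stating explicitly that both are required. Note in the plan that this overlaps with outcome b.

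The cost is wording in items 12 and 20a. Item 18a already provides the orders, referrals and dates in both arms, so no new data are needed. The registration table lists the trial as recruiting, so the change may need a formal amendment with ethics approval under item 25. It is best made before outcome data are examined by arm.
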